### 8.2.7.2 2nd visit 2/during surgery (Day 0)

- (1) Examining vital signs;
- (2) Intraoperative observation records;
- (3) Use of device;
- (4) Recording concomitant medication/treatment;
- (5) Monitoring of adverse events and serious adverse events;
- (6) Recording device defects;
- (7) Recording protocol deviations;

### 8.2.7.3 $3^{rd}$ visit 3/after surgery (Day 7 ± 2 days)

- (1) Examining vital signs;
- (2) Conducting laboratory examinations (blood routine, coagulation routine, blood biochemistry);
- (3) Conducting postoperative imaging examinations (angiography, thoracoscopy) ;
- (4) Postoperative follow-up observation;
- (5) Recording concomitant and combined medications;
- (6) Recording adverse events and serious adverse events;

Recording protocol deviations;

## 8.2.7.4 $4^{\text{th}}$ visit/after surgery (Day 30 ± 5 days)

- (1) Examine vital signs;
- (2) Conducting postoperative imaging examinations (angiography, thoracoscopy) ;
- (3) Postoperative follow-up observation;
- (4) Recording concomitant and combined medications;
- (5) Monitoring adverse events and serious adverse events;
- (6) Recording protocol deviations;

#### 8.2.8 Concomitant medication/treatment management

If a subject takes medication or therapeutic measures that caused the AE for various reasons during the study, such situation shall be recorded in the case report form (CRF) by investigators for reference.

- (1) Prohibited therapies: Products with similar efficacy to the study medical device and the control device are prohibited for use by all subjects during the clinical trial.
- (2) Allowable treatment: The treatment with other drugs or therapeutic measures required due to underlying diseases, concomitant diseases or adverse events should be recorded in the original medical records in

detail, including the name, dosage, usage of the drug and the name, usage and frequency of the therapeutic measures.

(3) The generic name, type, dose, frequency, route of administration and days of administration of other drugs used by the subjects as well as the name, method and frequency of treatment should be recorded in detail. The information is used to evaluate the possible bias on clinical trial results.

#### 8.2.9 Case report form completion

Case Report Form (CRF) is a document designed according to the clinical protocol to record the data of each subject during the trial. The correct completion of case report form will help to make a correct judgment on the trial results. Each investigator should complete the case report form carefully and pay attention to the following points:

- (1) Required fields on the CRF must not be left blank;
- (2) When completing the CRF, be sure to make the unit of test results consistent with the unit filled in;
- (3) All data on the CRF should be derived from original documents and be consistent with the original documents;
- (4) The investigator should complete and sign the CRF within 2 weeks after each subject completes relevant examinations, which is for overall monitoring by the clinical research associate;
- (5) If there is any uncertainty in the filling process, please communicate with the sponsor in a timely manner.

#### 8.3 Monitoring Plan

The sponsor shall, in accordance with the requirements of *Good Clinical Practice for Medical Devices*, select the qualified monitor to perform monitoring responsibilities for all the participating institutions. The monitoring frequency of each participating institution will be adjusted according to the speed of subject recruitment and subject number in each institution participating in the study. The monitor will complete the following responsibilities:

- Confirming that the clinical trial institution has been equipped with appropriate conditions before the trial, including qualified staffing and training, complete laboratory equipment, good working condition, expected to have a sufficient number of subjects, and investigators familiar with the trial requirements;
- (2) Monitoring whether the clinical trial institutions and investigators abide by relevant regulations, this specification and clinical trial protocol before, during and after the trial;
- (3) Confirming that each subject has signed the ICF before participating in the clinical trial, and that the inclusion of subjects as well as the progress of the trial are well known; monitoring and recording the failure follow up, non-conducted trial, non-conducted examination by the investigators, and whether the errors and omissions are corrected; for the revised ICF, confirming that the clinical trial process is not

completed and the affected subjects have re-signed the ICF;

- (4) Confirming that all the CRFs are correctly filled in and consistent with the original data; that all the errors or omissions have been corrected or explained, which have been signed and dated by the investigators; and that the disease type, total number of cases and gender, age and therapeutic effect in each trial have been confirmed and recorded;
- (5) Confirming that the subject withdrawing from the clinical trial or non-compliant with the requirements set forth in the ICF is recorded and discussed with the investigators;
- (6) Confirming that all adverse events, complications and other device defects are recorded, and serious adverse events and device defects that may cause serious adverse events are reported and recorded within the specified time;
- (7) Monitoring the supply, use, maintenance, transportation, reception, storage, distribution, processing and recovery of investigational medical device samples;
- (8) Supervising the regular maintenance and calibration of relevant equipment during the clinical trial;
- (9) Ensuring that all the documents related to the clinical trial received by the investigators are of the latest version;
- (10)Submitting a written report to the sponsor after each monitoring, which shall include the name of the monitor, date of monitoring, time of monitoring, place of monitoring, content of monitoring, name of the investigator, completion status of the project, existing problems, conclusions, and corrections to errors and omissions, etc.

## 9. Statistical Considerations

#### 9.1 Statistical Design, Methods and Analysis Procedure

This study is a prospective, multi-center, stratified block randomization, incomplete blinding, parallel positive control and non-inferiority test. All statistical analysis methods are detailed in the statistical analysis plan. The first draft of the statistical analysis plan will be formed after the trial protocol and case report forms are finalized and will be finalized before database lock.

## 9.2 Sample Size Calculation

#### 9.2.1 Total sample size

164 subjects are planned to be enrolled in this clinical trial. The sample size determination process is as follows:

This clinical study is a parallel positive control clinical validation design. The "device cutting and anastomosis success rate" is adopted as the basis for sample size estimation. Based on literature review , a

total of 160 patients were included in the study. All patients underwent thoracoscopic surgery with Johnson & JohnsonTM Echelon linear cutter stapler. During the surgery, 8 patients were converted into thoracotomy. Only 1 case of conversion to thoracotomy was resulted from linear cutter stapling failure. The other reasons were: intraoperative pulmonary artery bleeding in 3 cases, pulmonary vein bleeding in 1 case, lymph node metastasis or lymph node calcification and adhesion in 2 cases, and pulmonary artery anatomical malformation in 1 case. Therefore, when the similar device was used for VAT anatomical lobectomy (segmentectomy), the success rate of device cutting and anastomosis was up to 99.38% (1/160). The clinical investigators participating in this trial determined that the "device cutting and anastomosis success rate" of this clinical trial was conservatively estimated to be 97%, with a clinical non-inferiority margin of -10% based on the relevant literatures and considering the clinical practice. The parameters were set as follows:  $\alpha = 0.025$  (one-sided),  $\beta = 0.2$ ,  $\delta = -10\%$ , and the ratio of test group and the control group was 1:1. The formula of sample size estimation for non-inferiority clinical validation is adopted, and the sample size required in each group is at least 65 cases. The calculation formula and correction formula are as follows:

$$n_{3} = \frac{(\pi_{A}(1 - \pi_{A}) + \pi_{B}(1 - \pi_{B}))(Z_{1-\beta} + Z_{1-\alpha})^{2}}{((\pi_{A} - \pi_{B}) - d)^{2}}$$
$$n_{4} = \frac{n_{3} \left\{ 1 + \left[1 + \frac{4}{(\delta n_{3})}\right]^{\frac{1}{2}} \right\}^{2}}{4}$$

Considering that the number of subjects who may drop out or be lost to follow-up during clinical validation is about 20%, the sample size of each group is expanded to 82 cases, and the total sample size required for the two groups is 164 cases.

#### 9.2.2 Number of cases for clinical trial of each disease and reasons for determination

For the patients accepting anatomical lobectomy (segmentectomy) in this trial, the number of cases for each disease in the clinical trial is not specified.

#### 9.2.3 Minimum and maximum number of subjects in each clinical trial institution and reason

A total of 164 subjects are planned to be enrolled in this clinical trial, and a total of 5 clinical trial institutions are planned to participate in this trial. In the trial, the sample balance in each site should be maintained as far as possible. In combination with the total sample size and the number of participating clinical trial institutions, considering different number of disease sources in each center and possible difficulties in individual centers, each clinical trial institution should recruit at least 16 subjects but no more than 60 subjects.

#### 9.3 Significance Level and Power of Clinical Trial

Significance level  $\alpha$  (one-sided) = 0.025 with 80% power.

#### 9.4 Expected Dropout Rate

Version No.: 1.1/Version date: 20190325 Clinical Trial on Performance and Safety of Disposable Powered Articulating Endoscopic Linear Cutter Stapler in Total-Thoracoscopic Anatomic Lobectomy (segmentectomy)

A 20% dropout rate is expected during sample size estimation.

This drop-out rate refers to the proportion of subjects who finally can not be included in the primary analysis. Drop-out subjects refer to those confirmed by the principal investigator with serious protocol violation (affecting the main evaluation/efficacy evaluation). The following conditions may be included, but not limited to: the subject violates the inclusion and exclusion criteria; the subject does not receive any study device; the subject receives the concomitant medication/device prohibited by the protocol; the data of main evaluation indicators are missing; the subject fails to obtain any data after randomization; the subject fails to complete the follow-up visit according to the regulations.

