#### 8.1.3 Selection of test method and reasons

This clinical trial is a "prospective, multi-center, stratified-block randomization, incomplete blinding, parallel positive control, non-inferiority test".

- (1) Prospective: A research method that tracks from the present to the future. Prospective studies can clarify the causal relationship; uniform diagnostic, detection, and evaluation criteria can be available for the obtained data, the data processing therefore is controllable.
- (2) Multi-center: 5 clinical trial institutions were selected to conduct this clinical trial. The application of multi-center trial can allow to obtain more cases than those of single-center trial in the same time, the clinical trial time therefore can be shortened; since the multi-center trial is completed by different regions, different trial centers and many clinical researchers, the conclusion therefore is often widely representative.
- (3) Stratified block randomization: This trial adopts the stratified block randomization method (with the study site as the stratification factor) and the randomization envelope to randomize the subjects who are screened successfully. The randomized-grouping time is that before the surgery. Randomized grouping ensures that, except for treatment factors, other non-treatment factors that may have confounding effect are kept consistent in each group as far as possible, so as to ensure the balance of baseline of each group; randomized-grouping allows each subject to have equal opportunity to be assigned to the test group or control group.
- (4) Incomplete blinding: Since the investigational medical device and the control medical device are different in appearance, while the subjects are under anesthesia during the operation, the grouping arrangement can not be known. Therefore, the method of incomplete blinding is used, that is, the investigators knows the grouping result, while the subject does not know the grouping result. Blinded data review is also required at the same time. Incomplete blinding can minimize the bias caused by "placebo effect", and make the evaluation of adverse reactions by subjects more objective.

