#### (7) Incidence of device defects

**Definition:** An test device defect that occurs during the course of a clinical trial. "Staple pop" due to human factors (e.g., incorrect reload selection) is not a defect of the device.

Measurement time: During the whole process of clinical trial.

**Calculation formula:** Incidence of device defect = number of device defects/total number of devices  $\times$  100%.

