## 9.7.2 Missing, unused, or incorrect data (including dropouts and withdrawals) and unreasonable data

All missing, unused or incorrect data (including dropouts and withdrawals) and unreasonable data will be discussed and finally determined by the investigators and biostatistician in the data review stage. The basic statistical principles for the processing of these data are as follows:

- (1) The details of each drop-out case shall be described, and the drop-out between the test group and the control group shall be compared using Pearson  $X^2$  test or Fisher exact test;
- (2) Missing data at baseline shall not be estimated;
- (3) Missing values of main evaluation indicator (success rate of device cutting and anastomosis) shall not be estimated;
- (4) Missing values of secondary evaluation indicators shall not be estimated;
- (5) The wrong and unreasonable data shall be regarded as missing values;
- (6) Missing values for all safety measures shall be estimated using the worst case;
- (7) Sensitivity analysis shall be performed on the safety data set for all the safety evaluation indicators after treatment.

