## 16.1.3 Significant protocol deviations

- The subject does not meet any of the inclusion criteria or meets any of the exclusion criteria but is included in the trial.
- (2) Subjects, who meet the criteria for discontinuation during the trial, do not withdraw from the trial. Conditions that should lead to premature discontinuation of the trial include: laboratory test becomes significantly abnormal; the patient withdraws consent; the patient is pregnant; the patient experiences an endpoint event or the patient does not meet criteria to enter the next phase of the study.
- (3) The examination on safety indicators, primary efficacy indicator or key secondary efficacy indicator are not conducted as required by the protocol, thus affecting the scientificity of the study. Including: ① The above examinations are performed outside the time window specified in the protocol, which constitute an important protocol deviation when the data of the primary or key secondary efficacy indicators become inappropriate for statistical analysis; ② The specific requirements of the protocol for examination operation are not met; ③ The examination of safety indicators is not performed, which makes the patient faces safety risks.
- (4) The subject receives incorrect investigational device to the extent that it affects the subject safety or statistical analysis. For example, the device model does not match the use.
- (5) Any serious violation of the principles of GCP in the implementation of the protocol. The main categories include: ① inappropriate process of obtaining informed consent, such as obtaining informed consent by unauthorized researchers; failure to obtain informed consent from patients again or serious delay in obtaining informed consent again after the update of informed consent version; irregular completion/signing of informed consent form (e.g., incomplete signature/date, selection of questions not completed by subjects themselves, signing untrue dates, etc.); existing evidence indicating that the

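### Exclusion from the primary analysis is confirmed by an unblinded role on an open-ended list, and the plan does not reconcile this with the blinded data review it requires

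*Combined protocol and SAP*

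**What the plan says.** **Who excludes.** Section 9.4 equates the 20% dropout rate with the share of subjects who cannot enter the primary analysis, and adds: "Drop-out subjects refer to those confirmed by the principal investigator with serious protocol violation". The violation must affect the main or efficacy evaluation. The examples are stated to be non-exhaustive; they include missing primary data and follow-up not completed as required.

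**Who settles problem data.** Under 9.7.2, missing, unused, incorrect and unreasonable data, dropouts included, "will be discussed and finally determined by the investigators and biostatistician in the data review stage". Wrong or unreasonable values are treated as missing (item 5), and missing primary values are not estimated (item 3). Under 9.9 the per-protocol set (PPS) requires no serious deviation and no missing primary indicator. The PPS is called primary for efficacy, although the full analysis set (FAS) is also given an efficacy role.

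**What they know.** Sections 8.1.3(4) and 8.2.4 state that investigators are not blinded. Under 8.1.7.1 the primary endpoint is judged during surgery, and investigators decide whether a conversion to thoracotomy was caused by the stapler.

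**The safeguard.** Section 8.1.3(4) adds: "Blinded data review is also required at the same time". No section says who is blinded, to what, or how. Section 10.4 has the analysis sets settled before lock, with the lock confirmed by investigators, sponsor and project team.

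**Later events.** Section 8.1.8(5) classes staple-line adverse events as serious adverse events (SAEs). Section 8.1.6.9 makes an SAE a drop-out criterion.

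**The concern.** In a non-inferiority trial, leaving out failures on the test device moves the estimate towards the conclusion the sponsor wants. The usual protection is that whoever assigns subjects to analysis sets cannot see arm or outcome. Here the confirming role is unblinded, the list of grounds is open, and the promised blinded review is not connected to the decision.

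Two routes out of the primary analysis can be read directly from the text:

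1. A primary value is ruled wrong or unreasonable (9.7.2), so it becomes missing and is not estimated, and the subject cannot enter the PPS (9.9).
2. A staple-line adverse event counts as an SAE (8.1.8(5)), the SAE is a drop-out criterion (8.1.6.9), and incomplete follow-up is a ground in 9.4. The primary endpoint was already observed in surgery, so an event linked to device failure can remove a known outcome.

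Error control of the single registration claim is at stake.

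**Working it through.** **Inputs.** Section 9.3: "one-sided) = 0.025 with 80% power". Section 9.2.1: success "conservatively estimated to be 97%, with a clinical non-inferiority margin of -10" percentage points, and "the ratio of test group and the control group was 1:1". Section 9.5: non-inferiority holds if the lower 95% limit for test minus control exceeds -10%; no interval method is named.

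**The plan's own figure.** n3 = 2 × 0.97 × 0.03 × (0.8416 + 1.9600)² / 0.10² = 45.7. The correction formula with |δ| = 0.10 gives n4 = 64.1, hence 65 per arm. 65 / 0.80 = 81.25, hence 82 per arm and 164 in total. The stated sizes reproduce. The allowance for exclusion is 82 - 65 = 17 per arm.

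**How close the result can be.** Suppose 82 per arm, 2 control failures (80/82 = 97.6%) and 5 test failures (77/82 = 93.9%). The Newcombe lower limit is d - √[(pT - lT)² + (uC - pC)²], where l and u are Wilson limits.

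- All subjects kept: d = -3.66 points, lT = 86.51%, uC = 99.33%. The limit is -3.66 - √(7.40² + 1.77²) = -11.3%, so non-inferiority is not shown.
- One failed test subject removed (77/81 = 95.1%): d = -2.50 points, lT = 87.98%. The limit is -2.50 - √(7.08² + 1.77²) = -9.8%, so non-inferiority is declared.

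With uncorrected Wald, 5 test failures already pass (-9.8%). The change comes at 6 failures (-11.4%), where one removal is again enough.

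**Error rate on the margin.** The true rates are set to 87% v 97%. For k = 0 to 3 assumed removals, the joint binomial probabilities of all outcomes whose lower limit exceeds -10% are summed after min(k, failures) failed test subjects are taken out.

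| 82 per arm, test-arm removals only | k = 0 | k = 1 | k = 2 | k = 3 |
|---|---|---|---|---|
| Newcombe | 2.1% | 4.7% | 8.6% | 13.5% |
| Continuity-corrected Wald | 1.9% | 4.3% | 8.7% | 15.6% |
| Range, adding Miettinen-Nurminen | 1.9-2.1% | 4.3-4.7% | 7.5-8.7% | 13.5-15.6% |
| Uncorrected Wald | 4.3% | 8.7% | 12.5% | 20.9% |

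Uncorrected Wald, which 9.5 does not rule out, is above 2.5% before any removal. Starting from 65 per arm, the values for k = 0, 1, 2 are 2.3%, 4.5% and 9.7% (Newcombe) and 4.1%, 9.1% and 16.6% (uncorrected Wald).

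**Even-handed exclusion.** If the same number of failures leaves each arm (82 per arm, Newcombe), k = 1, 2, 3 gives 2.8%, 3.8% and 5.0%.

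**The case against.** **The illustration is one-sided.** It removes failures from the test arm only. Equal removal from both arms has a much smaller effect, as shown above. At 87% success about 11 test failures are expected (82 × 0.13 = 10.7), so in that scenario two removals change the verdict in only about 6.5% of trials (8.6 - 2.1). This stands as a limit on the size. It does not answer the point, because deciding with the arm known is exactly what allows one-sided removal.

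**Blinding may still be possible.** A reader might infer that the review cannot be blind. The documents do not support that. The biostatistician shares the decision in 9.7.2 and is nowhere said to be unblinded, 10.4 settles the sets before lock, and 9.1 defers methods to a separate analysis plan whose text is not in the material reviewed. Nor is the principal investigator said to operate in every case: Section 24 defines the role as team leader. What remains is that the confirming role is unblinded and 9.4 is not reconciled with 8.1.3.

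**Reload choice.** A reader might also infer that a failure blamed on the wrong reload is a listed ground for exclusion. Section 16.1.3(4) gives as an example of a significant deviation: "For example, the device model does not match the use". That concerns the device model, applies only where safety or analysis is affected, is not in the 9.4 list, and is nowhere mapped to PPS exclusion. Section 8.1.8(7) says that staple pop "due to human factors (e.g., incorrect reload selection) is not a defect of the device", but it defines a safety indicator and does not alter the primary endpoint. Extending 16.1.3(4) to reloads is possible, since the protocol speaks of reload models, but it is inference.

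**Other protection.** The FAS would keep a treated failure with recorded data, and 8.1.7.1 requires video of the cutting and anastomosis. But 9.9 calls the PPS primary for efficacy, 9.5 does not require success in both sets, and no section uses the video to assign analysis sets. Both help in part; neither is a stated safeguard.

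**Conclusion.** The point holds. As written, a subject with a test-arm failure can be left out of the primary analysis by a decision taken with arm and outcome known, and an SAE or incomplete follow-up can remove an endpoint already recorded in surgery.

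On the margin, one such removal roughly doubles the false-claim rate, from about 2% to 4.3-4.7%, and three raise it to 13.5-15.6%. These figures assume 82 per arm, 87% v 97%, removal of test-arm failures only, and one of the three interval methods in the range row. The number of removals is assumed, not taken from the documents, and nothing here suggests that any such removal took place. With even-handed removal the rate is 2.8-5.0% (Newcombe, one to three per arm).

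The conclusion does not depend on the reload reading or on the review being impossible to blind.

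**What to change.** **In 9.4, 9.7.2 and 9.9:**

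- Investigators supply the facts of each deviation and do not decide analysis sets.
- Before database lock, the data manager and biostatistician assign the sets against a closed list of exclusion grounds. They work from a listing with arm, device and reload model, and outcome value removed, but with a flag for whether the primary outcome is recorded. They sign it before those fields are merged back.
- A recorded intraoperative primary outcome is never set to missing or excluded because of a later SAE, withdrawal or missed follow-up, or because of the device or reload model chosen after allocation.

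**Reconcile** 8.1.6.9, 8.1.8(5), 9.4 and 9.9 for the purpose of the analysis sets, including which set carries the non-inferiority test. State in 8.1.3(4) that the masked assignment is the blinded data review. This concerns analysis only and takes no position on clinical withdrawal. Section 8.1.8(7) needs no change for this point.

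**Cost.** Protocol and analysis-plan wording, and one masked listing from existing staff; no more subjects or data. The downside is that a few subjects with deviations stay in the PPS.
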